Quantitative Analysis. Quantitative data from surveys and study databases will be summarized using descriptive statistics including frequencies, proportions, measures of central tendency (mean and median), and variability (standard deviation and interquartile range) along with data visualization methods, such as frequency tables, bar charts, line graphs, and scatter plots to understand implementation and effectiveness outcomes. 95% confidence intervals will be calculated when estimating proportions and means. Change from baseline to each post-intervention on effectiveness measures and mantram use will be calculated overall and by group (self-directed vs supported). Wilcoxon signed rank test and rank sum test will be used to examine the change in each group and compare the change between two groups. Linear mixed effects model will be used to examine the trajectory of change from baseline to post-intervention.

Qualitative analysis. Interviews will be recorded and transcribed. All qualitative data will be coded using a rapid qualitative data analytic approach. Unique and common themes across the two groups will be compared. Data analysis will be led by Drs. [name] and [name] and will also include qualitatively-trained members of the research team.

A matrix approach will be used to triangulate data from quantitative and qualitative sources. We will use a joint display analysis to support the integration of different data sources and types. Unique and common themes emerging across the two groups (self-directed and supported) will be identified and described.

Sample size. As a feasibility study, the sample size was not projected to ensure enough study power for hypothesis testing. We assessed the effect size of the effectiveness measures (e.g., PCL-5) that can be detected with the planned sample size and 80% power. The effect size for change in outcome from baseline to post treatment in each intervention group and for overall was estimated based on a paired t-test. With a sample size of 20 per group and 40 in total, we could detect an effect size of 0.66 and 0.45, which are moderate effect sizes. To compare the outcome change between the self-directed and supported groups, we could detect a large effect size of 0.91 for the difference with 20 subjects per group. This effect size would be clinically meaningful thus signaling the need for additional study. The sample size assessment was also conducted for assessing feasibility measures (e.g., initiation rate). First, we assessed the precision of estimates based on projected sample size. We considered a range of target rate from 0.60 to 0.90 and estimated the width of the 95% exact binomial confidence interval for overall and for each intervention group. If an estimated intervention initiation rate is 0.80, a sample size of 40 (total) and 20 (per intervention group) will produce a two-sided 95% confidence interval with a width of 0.243 and 0.335, respectively. If an estimated intervention initiation rate is 0.90, the width of the 95% CI is reduced (becomes more precise) with the same sample size projected above.

BIBLIOGRAPHY AND REFERENCES CITED

- Almklov, E. Shi, S., Pittman, J.O.E., Heppner, P., Afari, N., [name], L. (submitted). Characterizing Veteran Responses on the Brief Personal Health Inventory to Inform Whole Health Care. *Psychological Services*.
- Bastien, C. H., Vallières, A., & Morin, C. M. (2001). Validation of the insomnia severity index as an outcome measure for insomnia research. *Sleep Medicine, 2*(4), 297–307.
- Blevins, C. A., Weathers, F. W., Davis, M. T., Witte, T. K., & Domino, J. L. (2015). The Posttraumatic Stress Disorder Checklist for DSM-5 (PCL-5): Development and Initial Psychometric Evaluation. *Journal of Traumatic Stress, 28*(6), 489–498.
- Borkovec, T. D., & Nau, S. D. (1972). Credibility of analogue therapy rationales. *Journal of Behavior Therapy and Experimental Psychiatry, 3*(4), 257–260.

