Feasibility and Acceptability of Mobile Mantram
Repetition Program for Veterans With PTSD
(IVI 22-115)

NCT05998967

August 12, 2021

SPECIFIC AIMS

Easily accessible interventions to address post-traumatic stress disorder (PTSD) can play critical role in reducing PTSD and associated symptoms in Veterans, especially for those who remain symptomatic after treatment with other evidence-based interventions, those who prefer complimentary and integrative therapies, or those who have difficulty accessing traditional face-to-face mental health services. The value of these programs is their ability to provide Veterans with more options in their recovery journey and to reach a broad range of Veterans across multiple settings, including remote rural contexts.

The Mantram Repetition Program (MRP) is a meditation-based practice that consists of the repetition of a spiritual word, one-pointed attention, and slowing down. MRP has been shown to reduce stress in several high-risk populations, and two large randomized, controlled studies show that MRP reduces PTSD symptoms among Veterans. A brief, web-based, self-directed version of MRP has been developed to increase the accessibility of evidence-based PTSD treatment. This version of MRP was tested in a pilot study with undergraduate students, demonstrating its ease of use and success in getting students to engage with the practice. The proposed mixed method study will use the Reach, Effectiveness, Adoption, Implementation, Maintenance (RE-AIM) framework to evaluate the mobile MRP in Veterans with PTSD in two conditions: self-directed and with text/phone support. Data from this pilot study will inform the refinement of the MRP delivery strategy and the development of a full-scale trial to test its effectiveness and implementation outcomes, as well as barriers and facilitators, and other contextual factors.

Aim 1. To assess the reach and implementation of the mobile Mantram Repetition Program using a mixed methods approach focusing on feasibility, acceptability, appropriateness, and facilitators of and barriers to program implementation.

Aim 2. To compare Veterans who are self-directed users of mobile MRP versus Veterans who receive text and phone support in terms of engagement with the intervention and change in PTSD and associated symptoms.

BACKGROUND AND SIGNIFICANCE

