eScreening is a web-based, patient-facing screening and information-provision system developed with Veteran and staff feedback that allows for the rapid capture of self-report data and has been shown to improve the quality of documentation and access to care (Pittman et al., 2019). Across multiple VHA facilities, eScreening has been utilized over 34,000 times with Veterans in Transition Care Management, primary care, and mental health settings; eScreening supports both screening and measurement-based deployment of evidence-based psychotherapy. In 2016, the eScreening program was named a Gold Standard Practice for diffusion throughout VHA by the Under-Secretary for Health (Elnahal et al., 2017). eScreening is available nationwide and is a promising platform for the delivery of MRP to Veterans.

The goals of this study are to (1) better understand mobile MRP by measuring reach, feasibility, acceptability, appropriateness, barriers and facilitators; and (2) compare effectiveness (i.e., mantram use, PTSD and associated symptoms) of self-directed MRP (i.e., used without support from a facilitator) to supported MRP (i.e., text/phone support provided by a facilitator) in Veterans with PTSD using the existing VA eScreening platform for delivery of the program.

This project is responsive to several HSR&D priorities. If successful, this program would enhance access to care, thereby increasing health equity through the utilization of virtual care. This project also targets PTSD and associated symptoms, including insomnia, important mental health issues prioritized by HSR&D. This project features meditation, which is of interest to an increasing number of Veterans and a potential component of the Whole Health approach, whereby Veterans may focus on overall wellness, including spirituality. Finally, this study uses eScreening, an electronic, self-report screening system, developed by our research group for data collection and access to the intervention videos. Consistent with the aims of the SWIFT-IVI program, we will pilot an implementation strategy in preparation for a future fully-powered implementation trial with the aim of rapidly deploying the MRP into routine practice.

METHODS

Study Design

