This study is a prospective, randomized trial assessing implementation and effectiveness outcomes of a brief, self-directed, web-based meditation training. We will employ a mixed-method convergent approach to collect and analyze data to inform future implementation of the MRP (Palinkas et al., 2019).

Participants

Participants will be 40 Veterans with PTSD residing in San Diego County, CA. These individuals will be recruited from VA clinics (self- and provider-referral) and through community outreach (e.g., advertisements). Eligibility is intentionally broad to approximate future real-world users of MRP.

Inclusion: Veteran, 18 or older, primary clinical complaint of PTSD, ability to access internet-enabled smart phone, tablet, or computer.

Exclusion: Cognitive impairment or mental health concerns that necessitate a higher level of care or interfere with the ability to consent or engage in study activities (serious mental illness, untreated alcohol or substance use disorder, serious suicidality or homicidality, marked cognitive impairment).

Interventions

MRP consists of four online training modules that were developed for a Veteran audience by [name], the developer of the intervention. They cover the basic intervention components: choosing a mantram, slowing down, attentional control and habit formation. These videos were created in conjunction with PsychArmor, Inc., a non-profit organization that provides training to multiple sectors who support Veterans and are available via internet (refer to Letter of Support from [name]). In the **self-directed condition**, enrolled Veterans will not be contacted unless they reach out using contact information in the weekly module. In the **supported condition**, Veterans will receive a daily text reminder to practice their mantram (e.g., "Did you find a moment to practice your mantram today? Please respond YES, NO or HELP if you would like to talk to one of our staff."). Those who answer in the affirmative will receive praise and an offer of support (e.g., "Great job! A regular practice happens one day at a time!"). Those who answer in the negative will receive brief encouragement and an offer of assistance (e.g., "You can repeat your mantram at any spare moment. Would you like to speak with a trainer about working it into your day?"). A request for help will be followed by a personal text and call by study staff.

Procedures

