Following provision of written informed consent and HIPAA authorization using a telehealth-based informed consent process, Veterans will confirm access to a study-compatible device (Internet-enabled smart phone, tablet or computer) and be administered a semi-structured interview (MINI) and brief cognitive screen (blind MoCA) via telephone by a trained Research Assistant (RA) to confirm eligibility. If deemed eligible, the Veteran will be randomly assigned to one of two conditions: self-directed MRP or supported MRP. Veteran involvement then proceeds as follows:

1. Veterans complete a brief assessment battery (see **Measures**) including demographics and mental health symptoms using eScreening.
2. Veterans access the training videos via eScreening.
 - a. Day 1: All complete a brief symptom screener (see **Measures**), watch a ~15-minute instructional video (#1) and answer comprehension and credibility questions about the video.
 - b. Days 2-7: *Supported condition only*: They are prompted daily to engage in meditation practice and may receive support toward that end (see **Interventions**).
 - c. Day 8: All complete a brief symptom screener and questions about meditation practice, watch a ~15-minute instructional video (#2), and answer comprehension questions about the video.
 - d. Days 9-14: *Supported condition only*: Daily prompts/support.
 - e. Day 15: All complete a brief symptom screener and questions about meditation practice, watch a ~15-minute instructional video (#3), and answer comprehension questions about the video.
 - f. Days 16-21: *Supported condition only*: Daily prompts/support.
 - g. Day 22: All complete a brief symptom screener and questions about meditation practice, watch a ~15-minute instructional video (#4), and answer comprehension questions about the video.
 - h. Days 23-28: *Supported condition only*: Daily prompts/support.

- Veterans complete a brief assessment battery about mental health symptoms and answer questions about the feasibility, acceptability, and appropriateness of mobile MRP (Weiner et al., 2017).

Data Collection and Measures

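### Is a measure of mantram use missing at entry and after the fourth module, so that the planned change analysis cannot be done?

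*Combined protocol and SAP*

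**What the plan says.** Mantram use is one of the outcomes on which the arms are compared. The goals paragraph in Background and Significance says the study will "compare effectiveness (i.e., mantram use, PTSD and associated symptoms) of self-directed MRP" with supported MRP, and Aim 2 compares the arms "in terms of engagement with the intervention and change in PTSD and associated symptoms". Under Data Analysis, Quantitative Analysis: "Change from baseline to each post-intervention on effectiveness measures and mantram use will be calculated overall and by group (self-directed vs supported"). Signed-rank tests are planned within groups, a rank-sum test between groups, and a mixed model for the trajectory. Descriptive summaries and 95% confidence intervals for proportions and means are planned as well.

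On collection, Procedures describes the entry battery as "including demographics and mental health symptoms using eScreening", with a pointer to Measures. Practice questions for everyone are listed on Days 8, 15 and 22. The last entry reads "Day 22: All complete a brief symptom screener and questions about meditation practice, watch a ~15-minute instructional video (#4"). Then come "Days 23-28: *Supported condition only*: Daily prompts/support" and a closing item: "Veterans complete a brief assessment battery about mental health symptoms and answer questions about the feasibility, acceptability, and appropriateness of mobile MRP". Table 1 and Implementation Measures name mantram use and the Mantram Use Scale, with eScreening surveys among the data sources, but give no administration times.

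**The concern.** A change score needs a first and a last value, and the schedule names neither for mantram use. The last listed report precedes video #4, so no listed report reflects the complete training. The gap cannot be filled from the text messages, because they belong to one arm: in the supported condition "Veterans will receive a daily text reminder to practice their mantram", while self-directed Veterans are not contacted unless they get in touch.

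If the closing survey really omitted the scale, use after full training would be lost for good. That outcome bears directly on the choice between self-directed and supported delivery. A second worry is that any baseline would precede the modules that teach how to choose a mantram. Most baselines might then be zero, and the within-group test would show little more than that some Veterans used what they were taught.

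**Working it through.** **1. The plan's own figures.** The Sample size section gives detectable effects of 0.91 (between arms, 20 per group), 0.66 (within a group of 20) and 0.45 (all 40) at 80% power. Noncentral-t calculations, with two-sided alpha 0.05 assumed because none is stated, give 0.909, 0.660 and 0.454. All three reproduce. None depends on when the Mantram Use Scale is given.

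**2. What Procedures lists for mantram use.**

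| Time | Both arms | Supported arm only |
|---|---|---|
| Entry battery, Day 1 | none named | none |
| Days 8, 15, 22 | practice questions, before that day's video | none |
| Days 2-7, 9-14, 16-21, 23-28 | none | daily text, YES/NO reply |
| Closing battery | none named | none |

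**3. Size on the literal reading.** Prompted days: 4 × 6 = 24. Prompted days after the last common report: 6, and 6/24 = 25%. Modules after it: 1 of 4.

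**4. Is Procedures an exhaustive list?** Compare it with the Measures sections:

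| Measure | Where it is planned | Named in Procedures? |
|---|---|---|
| Brief PHI | Table 1 and Effectiveness Measures; its change falls under the planned analysis | No. It covers physical well-being, daily life and nine areas of health, so it is more than a symptom measure |
| Satisfaction | Table 1 and Implementation Measures; includes the course as a whole, so it fits only after the modules | No |
| Qualitative interview | Table 1, Implementation Measures, Qualitative analysis | No |
| Mantram Use Scale | Table 1, Implementation Measures; mantram use is in the planned change analysis | No |

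Three other planned measures are missing from Procedures in the same way. Absence from that list is therefore weak evidence that a measure will not be collected.

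**5. What the analysis presupposes.** Calculating change in mantram use from baseline to post-intervention requires collection at both ends. A dedicated scale is named, apparently distinct from the weekly practice questions, and eScreening surveys are given as a source. The natural reading is that the scale sits in the two batteries. If the analysis wording instead refers to the weekly visits, Days 8, 15 and 22 are listed for both arms, and only the baseline and the final period are unnamed.

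**6. Would comparing final levels be better?** Let D = Y − B, with Y final use and B baseline use.
- If B = 0 for everyone, D = Y. The ranks are identical and the rank-sum test gives the same result. Nothing is gained.
- If some Veterans already use a mantram, suppose B and Y have equal variance σ² and correlation ρ. Then Var(D) = 2σ²(1 − ρ), against Var(Y) = σ². Change is the more precise when ρ > 0.5 and the level is when ρ < 0.5. The documents give no ρ, so neither has a demonstrated advantage. Comparing levels also leaves a chance imbalance in prior practice uncorrected.

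**7. The within-group test.** With all baselines zero and m users, the exact two-sided signed-rank p is 2 × 0.5^m: 0.0625 for m = 5 and 0.031 for m = 6. The chance of at least 6 users among 20 is 20% if true uptake is 20%, 58% at 30% and 87% at 40%. These figures shift with the assumptions. The documents do not specify an exact test. Under the uncorrected normal approximation, 5 untied users already give p = 0.043, and rejection at 30% uptake becomes 76%. The uptake rates are assumed, the scale's scoring is not given, and prior use is unknown. A significant within-group result would say little, but the planned proportions, means and confidence intervals already supply the informative summary.

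**The case for a change.** The strongest opposing case is practical. The closing item, unlike the entry item, carries neither open-ended wording nor a pointer to Measures. Someone building the surveys from Procedures alone, where practice questions appear on three named days and not at the end, could leave the scale out. Data not asked for cannot be recovered, the texts exist in one arm only, and adding an existing scale to an existing survey costs a few minutes of participant time.

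Part of this stands. The time points of the Mantram Use Scale are not written down, and nothing says that the weekly practice questions are that scale.

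The step from unnamed to uncollected does not stand. It would require staff to treat Procedures as complete, although it omits three other planned measures, and to ignore an analysis section that names mantram use. The stakes are also smaller than they first appear. Engagement in Aim 2 is not defined as mantram use alone. Video completion, which counts only with a correct comprehension answer, covers the fourth module in both arms, and the weekly reports give common data over the first three weeks.

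**Conclusion.** The concern identifies an unstated time point, not a missing measure. On the most literal reading, 6 of 24 prompted days (25%) and one of four modules would lack a common use report. That reading conflicts with the plan's own analysis, which needs a value at entry and at the end. Deciding which survey carries the scale is an ordinary set-up detail that staff would settle from the analysis section.

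The planned between-arm rank-sum comparison is sound whether baselines are zero or not, and the descriptive summaries and confidence intervals are already in place. Replacing change with level brings no gain in the first case and no shown gain in the second.

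This conclusion rests on two assumptions: that Procedures is shorthand, which its other omissions support, and that the surveys are built to serve the stated analysis. The study's size and purpose (40 Veterans, feasibility, not powered for hypothesis tests) also weigh against altering the plan on this point. No change follows.

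### For PCL-5, PHQ-9 and ISI the only explicit between-arm analysis is a rank-sum test on change: no between-arm difference with a 95% CI is specified, and baseline is not a covariate

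*Combined protocol and SAP*

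**What the plan says.** Aim 2 (Specific Aims) compares self-directed with supported users "in terms of engagement with the intervention and change in PTSD and associated symptoms". The analysis of the symptom part is in Data Analysis, Quantitative Analysis:

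- Change scores: "Change from baseline to each post-intervention on effectiveness measures and mantram use will be calculated overall and by group (self-directed vs supported").
- Tests: the signed rank test and "rank sum test will be used to examine the change in each group and compare the change between two groups".
- Model: "Linear mixed effects model will be used to examine the trajectory of change from baseline to post-intervention". No arm term, arm-by-time term, covariate or contrast is written.
- Intervals: "95% confidence intervals will be calculated when estimating proportions and means". A difference between arms is not named.

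The Sample size paragraph says that "the sample size was not projected to ensure enough study power for hypothesis testing". For the comparison of arms it says that "we could detect a large effect size of 0.91 for the difference with 20 subjects per group", and continues: "This effect size would be clinically meaningful thus signaling the need for additional study".

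**The concern.** The Sample size paragraph links the case for further study to the size of a between-arm effect, but a rank-sum p-value does not report a size. A pilot that disclaims power for testing and feeds a larger trial should lead with an estimate and its interval, with the test second. The plan already does this for feasibility rates, which are justified by CI width. The symptom comparison has no equivalent.

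The second issue is precision. PCL-5, PHQ-9 and ISI are effectiveness measures whose change from baseline is to be calculated, so a baseline score will exist for each. Subtracting it fixes the baseline slope at 1. Estimating the slope often gives a narrower interval from the same data.

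**Working it through.** **Inputs.** From the Sample size paragraph: 20 per arm, 80% power, detectable effect 0.91. From Effectiveness Measures: PCL-5 test-retest r = .84. This is the only correlation in the document. It is not a baseline-to-post correlation and serves only as an upper guide. Assumed: two-sided alpha 0.05, normal data, complete follow-up, baseline-to-post correlation rho from 0.3 to 0.84, and post/baseline SD ratio k. The document gives neither rho nor k for any scale. Effects and widths are in units of the SD of change.

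**1. The plan's own figure.** Two-sample t-test on change, 38 df, noncentrality d/√(2/20). Power reaches 80% at d = 0.909, so the stated 0.91 is reproduced (one-sided alpha would give 0.80). This is a t-test figure. In simulation with normal data, the planned rank-sum test has about 78% power at this effect.

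**2. Interval for the unadjusted difference.** Mean width = 2 × t(38) × c4 × √(2/20) = 2 × 2.024 × 0.9934 × 0.3162 = 1.272, where c4 is the ratio of the expected sample SD to the true SD. The half-width is 0.636, so an observed 0.91 gives 0.91 ± 0.636, or 0.27 to 1.55.

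**3. Baseline as covariate.**

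Var(adjusted)/Var(change) = (37/36) × [1 − (1 − rho·k)² / (1 + k² − 2·rho·k)]

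The factor 37/36 is the cost of estimating the slope. With k = 1 the bracket is (1 + rho)/2. For rho = 0.5 the ratio is (37/36) × 0.75 = 0.771, and the width is 2 × t(37) × c4 × √(0.1 × 0.771) = 1.12.

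| rho (k = 1) | Variance ratio | 95% CI width | Narrower by | Detectable at 80% |
|---|---|---|---|---|
| unadjusted | 1 | 1.27 | – | 0.91 |
| 0.3 | 0.668 | 1.04 | 18% | 0.74 |
| 0.5 | 0.771 | 1.12 | 12% | 0.80 |
| 0.7 | 0.874 | 1.19 | 6.5% | 0.85 |
| 0.84 | 0.946 | 1.24 | 2.7% | 0.88 |

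**4. Where the gain disappears.** From the formula, adjustment lowers the variance only if |1 − rho·k| exceeds √(1/37) = 0.164 times SD(change)/SD(baseline). Inside that zone the interval is slightly wider: +0.6% at k = 1.1, rho = 0.84; +1.1% at k = 1.5, rho = 0.6; +1.4% at k = 1.2, rho = 0.84. The maximum, at rho·k = 1, is a variance ratio of 37/36 and, with t(37) replacing t(38), a mean width 1.45% larger. Beyond the zone adjustment helps again (3.4% narrower at k = 1.5, rho = 0.84).

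**5. Simulation** (20,000 replicates, 20 per arm, effect 0.909, k = 1, rho = 0.3/0.5/0.7/0.84).

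- Normal data: rank-sum power about 78% throughout; adjusted model 93/89/85/82%. The Hodges-Lehmann interval is 1.31 wide throughout.
- Heavy-tailed residuals (t, 3 df): rank-sum 88/90/92/93%, adjusted model 93/90/87/86%. Hodges-Lehmann width 1.14/1.10/1.05/1.01, adjusted 0.98/1.05/1.12/1.17.
- Type I error is 0.047 to 0.051 for the rank-sum, t-test and adjusted analyses.

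**6. Loss to follow-up.** The student pilot cited in the Background had 87% follow-up; 0.87 × 20 = 17.4, so take 17 per arm. The unadjusted interval around 0.91 becomes about 0.22 to 1.60. The gain at rho = 0.84, k = 1 is 2.4%, and the penalty at k = 1.2, rho = 0.84 is about 1.75%.

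**The case against.** The strongest case against runs as follows.

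- *The plan does not report only a p-value.* It lists means, SDs, CIs for means and change by arm, from which the unadjusted difference and its interval follow by arithmetic. This is true and limits the first half of the point to a missing specification. It does not supply the adjusted estimate.
- *The mixed model was probably meant to compare arms.* It may have been, given Aim 2, but no arm contrast is written. If that was the intent, completing the model is an acceptable form of the fix.
- *Baseline adjustment is a preference here.* At the only documented correlation the gain is 2.7%, the larger gains rest on assumed correlations, and with heavy tails and high correlation the rank-sum analysis does better. These facts stand and are why the rank-based analysis should be kept. They do not make the change score the better lead: the possible loss is about 1.5% of width and the possible gain much larger.
- *The 0.91 is a detectable true effect, not a decision rule on the observed estimate.* It is correct that no formal rule is set. Even so, the paragraph says an effect of that size would signal further study, so readers will want the estimated size.

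**Conclusion.** The concern holds. The text specifies no between-arm estimate with an interval for the three symptom scales, and baseline is not used as a covariate. The need for an estimate and CI depends on no assumed correlation: at 20 complete cases per arm the unadjusted interval is about 1.27 SD of change wide, and it is wider with dropout. The gain from adjustment is conditional. It is 18% to 2.7% for rho from 0.3 to 0.84 with equal SDs and normal data, nil or slightly negative (up to about 1.5% at 20 per arm, about 1.75% at 17) when rho·k is near 1, and reversed in favour of the rank-based analysis under heavy tails at rho of 0.7 or above. No bias and no numerical error in the 0.91 is claimed. This is a change that should be made, with medium confidence because the document gives no baseline-to-post correlations or SDs.

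**What to change.** For PCL-5, PHQ-9 and ISI only:

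1. Make the between-arm analysis a linear model of the post score on arm and the same scale's baseline score, or a mixed model with a common baseline mean and a stated arm contrast at post. Report the adjusted difference with its 95% CI.
2. Keep the rank-sum test on change as sensitivity, with a Hodges-Lehmann estimate and 95% CI.
3. Confirm, or arrange, that the baseline battery is completed before the arm is disclosed. Procedures lists it after random assignment, and both the change score and the adjusted model need a baseline unaffected by arm.

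Do not extend this to mantram use (no baseline listed), the brief symptom screen (no post-treatment administration listed) or the Brief PHI (no total score defined).

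The cost is SAP wording for three scales and one clarification of sequence. The model uses one residual degree of freedom and relies on roughly normal residuals, which the retained rank-based analysis checks.

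### Do the detectable effects of 0.66, 0.45 and 0.91 need an allowance for Veterans without both baseline and post-intervention scores?

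*Combined protocol and SAP*

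**What the plan says.** The Participants section fixes enrolment: "Participants will be 40 Veterans with PTSD residing in San Diego County, CA". The sample size paragraph under Data Analysis opens with a disclaimer that "the sample size was not projected to ensure enough study power for hypothesis testing". It then reports, as an assessment, the effects "that can be detected with the planned sample size and 80% power".

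- Within each arm and overall, the method is given as follows: "change in outcome from baseline to post treatment in each intervention group and for overall was estimated based on a paired t-test". The result is "With a sample size of 20 per group and 40 in total, we could detect an effect size of 0.66 and 0.45".
- Between arms, "we could detect a large effect size of 0.91 for the difference with 20 subjects per group". No test is named for this figure.
- No significance level is given for any of the three.

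The Quantitative Analysis paragraph matches this focus on change: "Change from baseline to each post-intervention on effectiveness measures and mantram use will be calculated overall and by group". The planned tests of change are the Wilcoxon signed rank and rank sum tests, and a linear mixed effects model is planned for the trajectory. Under Procedures, the baseline battery comes after random assignment. After the last week of the programme, "Veterans complete a brief assessment battery about mental health symptoms" and answer the implementation questions.

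No section gives an expected dropout rate for Veterans, an enlarged enrolment, or a statement that complete data are assumed. The only retention figures for this self-directed format come from the undergraduate pilot in Background and Significance: 88% finished the intervention and 87% the follow-up assessment.

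**The concern.** A change score needs two measurements. If 40 Veterans are enrolled and some do not return the post-intervention battery, fewer than 40 change scores exist, and a detectable effect worked out for 20 per arm is too favourable. The baseline battery follows randomisation, so that score could be missing too. The document itself reports that about one in eight pilot students did not complete follow-up, and the sample size paragraph makes no use of it.

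The figure could be carried forward. The sentence after the 0.91 describes an effect of that size as clinically meaningful and as a sign that further study is needed, and the Specific Aims say that the pilot will inform a full-scale trial. A reader might therefore take 0.91 as what the study will be able to detect, when it is what the study could detect with no loss.

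**Working it through.** **Inputs.** Enrolment is 40 (Participants). The analysed numbers are 20 per arm and 40 overall, with 80% power and a paired t-test for the within-arm and overall figures (sample size paragraph). The two-sided alpha of 0.05 and the two-sample t-test on change behind 0.91 are inferred, because together they reproduce the printed values. Pilot follow-up is 87% (Background and Significance). Every other completion rate below is an assumption.

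**Formulae.** Power is the probability that a noncentral t variable exceeds the two-sided critical value. The noncentrality is λ = d × √n with n − 1 degrees of freedom for paired data, and λ = d / √(1/n₁ + 1/n₂) with n₁ + n₂ − 2 degrees of freedom for two arms. Each is solved for the d that gives 80% power.

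**Step 1: reproduce the plan.**

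- Paired, n = 20: d = 0.660, so λ = 0.660 × √20 = 2.95. Printed 0.66; power at 0.66 is 79.9%.
- Paired, n = 40: d = 0.454, so λ = 0.454 × √40 = 2.87. Printed 0.45; power at 0.45 is 79.3%.
- Two arms, 20 and 20: d = 0.909, so λ = 0.909 / √(1/20 + 1/20) = 2.87. Printed 0.91; power at 0.91 is 80.1%.

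The alternatives do not fit. One-sided 0.05 gives 0.577, 0.400 and 0.801. The normal approximation at two-sided 0.05 gives 0.626, 0.443 and 0.886. The printed figures are therefore correct for the numbers printed beside them.

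**Step 2: allow for loss.** 87% of 40 is 34.8, taken as 35 and split 17 and 18. The other rows show a range.

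| Completers per arm | Within arm | Overall | Between arms | Power at 0.91 |
|---|---|---|---|---|
| 20 / 20 | 0.66 | 0.45 | 0.91 | 80% |
| 18 / 18 (90%) | 0.70 | 0.48 | 0.96 | 76% |
| 17 / 18 (about 87%) | 0.72 / 0.70 | 0.49 | 0.98 | 74% |
| 16 / 16 (80%) | 0.75 | 0.51 | 1.02 | 70% |
| 14 / 14 (70%) | 0.81 | 0.55 | 1.10 | 64% |

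One Veteran lost (19 and 20) gives 0.92 and 79%. How five losses divide hardly matters: 16 and 19 gives 0.98, and 15 and 20 gives 0.99, with 73% to 74% power at 0.91.

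A rough check: the detectable effect grows roughly as the square root of the ratio of sample sizes, and 0.909 × √(40/35) = 0.97, close to the exact 0.98.

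**Step 3: compare with an approximation already in the figures.** The calculation uses t-tests, but the planned tests are rank tests. Under normality their relative efficiency is 3/π = 0.955, so 20 per arm behaves like 20 × 0.955 = 19.1. That gives about 0.68, 0.47 and 0.93 with complete data. The shift from 0.91 to 0.93 is larger than that from losing one Veteran (0.92), so the printed figures are approximate in any case.

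**Step 4: ask what depends on the figures.** The enrolment of 40 is not derived from them; the paragraph starts from 40 and reports what follows. No test, success criterion or stopping rule refers to them. This check covers the three effect sizes only, and not the confidence-interval widths in the same paragraph.

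**The case for a change.** The strongest case for a change is that the paragraph, having disclaimed power, still says what the sample can detect at 80% power, and a statement of that kind should carry its condition. The condition is not trivial. No rate for Veterans with PTSD is documented, 87% in students need not be the lower limit, and at 70% completion the power at 0.91 is 64%. The mixed model does not answer this, because the printed effects are for change scores and the planned rank tests of change also need both measurements. Stating the assumption, the alpha and the test behind 0.91 would cost a sentence or two and disturb nothing.

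The facts in that case stand: the assumption is real, it is unstated, and alpha is missing. What does not follow is that the plan needs correcting. Each effect is given with its n, so a statistician can see that nothing was deducted. With no Veteran rate to hand, any allowance would be borrowed, and learning how Veterans take up and stay with the programme is part of what a feasibility study is for. Substitute t-test figures at 87% would themselves rest on an inferred alpha and would still be slightly favourable for the rank tests. The remark about further study is commentary on a large effect. It sets no threshold against which the trial's result will be judged.

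**Conclusion.** The concern is factually right but calls for no change. The figures 0.66, 0.45 and 0.91 are correct for 20 per arm and 40 overall, and they describe the study with no loss. If completion matched the student pilot, they would be about 0.70 to 0.72, 0.49 and 0.98, with 74% power at 0.91. At an assumed 70% completion the between-arm figure would be 1.10, with 64% power. These values rest on t-tests at two-sided 0.05, which the plan does not state but which its own numbers imply, and on completion rates that the documents do not give for Veterans.

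This is an omitted detail in an illustrative calculation, within a study that says it was not sized for hypothesis tests. Filling it in would leave enrolment, procedures, analyses and conclusions as they are. When results are reported, the actual numbers with both scores and the widths of the confidence intervals will show what the study could resolve, and a full-scale trial can be sized with the retention observed here.
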